4.1 Rationale for study design

- The design of this study addresses the primary objective of assessing the efficacy of PEAR-004 in subjects with schizophrenia and takes into account the novel use of a digital therapeutic to treat disease.
- Bias will be reduced by randomizing subjects to PEAR-004 or sham. Only subjects randomized to Group A will have access to the full clinical content and treatment logic of PEAR-004 and its therapeutic components.
- Raters will be blinded to randomization assignment.

4.2 Rationale for duration of treatment

No investigational medicinal product will be provided in this study; subjects will continue on their prescribed clinician-directed pharmacotherapy.

PEAR-004 is an investigational medical device, which is a prescription digital therapeutic.

The duration of treatment of 12 weeks with PEAR-004 or sham was selected based on the standard treatment duration for antipsychotic drug trials in schizophrenia to assess short-term benefit.

4.3 Rationale for choice of control

Digital therapy with PEAR-004 involves interaction with an application on a smartphone. To control for nonspecific effects of engagement with a smartphone, a sham application will be provided which does not deliver active coping skills derived from evidence-based psychosocial interventions. The sham app will include notifications 3 times per day, and when the app is opened it will display a prescription timer for the remaining duration of app availability.

4.4 Purpose and timing of interim analyses

Interim analyses may be conducted to support decision making concerning the current clinical study, the sponsor's clinical development projects in general, or in case of any safety concerns.

4.5 Risks and benefits

There is no benefit expected for subjects participating in this study.

Appropriate eligibility criteria and stopping rules are included in this protocol.

The risk to subjects in this trial may be minimized by compliance with the eligibility criteria and study procedures, as well as close clinical monitoring.

5 Population

Approximately 102 subjects will be enrolled in the study and randomized.

The investigator must ensure that all subjects being considered for the study meet the following eligibility criteria. No additional criteria should be applied by the investigator, in order that the study population will be representative of all eligible subjects.

Subject selection is to be established by checking through all eligibility criteria at screening. A relevant record (e.g. checklist) of the eligibility criteria must be stored with the source documentation at the study site.

Deviation from any entry criterion excludes a subject from enrollment into the study.

5.1 Inclusion criteria

Subjects eligible for inclusion in this study must meet **all** of the following criteria:

1. Signed informed consent must be obtained prior to participation in the study.
2. Healthy male and female subjects 18 to 65 years of age, inclusive, and in good health as determined by medical history, physical examination, and vital signs at screening
3. SCID-based DSM-5 diagnosis of schizophrenia and a total PANSS score > 60
[Kay et al 1987](#)
4. Proficient in English at 5th grade reading level or higher, in the judgement of the investigator
5. Capable of using a mobile device (compatible with PEAR-004) and using common applications, in the judgement of the investigator

5.2 Exclusion criteria

Subjects meeting any of the following criteria are not eligible for inclusion in this study.

1. Major change in primary antipsychotic medication in the prior 4 weeks before screening (e.g., switching to a new agent or a dose adjustment within two weeks of randomization)
2. Planning to move out of the geographic area within 3 months
3. Unable to use English to participate in the consent process, the interventions or assessments
4. Inability to comply with study procedures, due to severe medical conditions or otherwise
5. Meet DSM-5 diagnosis for a current episode of major depression, mania, or hypomania in the past month
6. Meet DSM-5 diagnosis for a current moderate or severe alcohol or cannabis use disorder in the past 2 months
7. Meet DSM-5 diagnosis for a current substance use disorder (other than alcohol or cannabis) in the past 2 months
8. Considered high risk for suicidal behavior based on ISST-Plus score at screening, or in the judgement of the investigator
9. Previously participated in a clinical study involving PEAR-004

6 Treatment

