Secondary Objectives	
Objective 1: To evaluate the efficacy of PEAR-004 as an adjunct to existing clinician-directed pharmacotherapy to reduce positive symptoms of schizophrenia by change in Positive and General Psychopathology PANSS scores
 
Objective 2: To evaluate the efficacy of PEAR-004 as an adjunct to existing clinician-directed pharmacotherapy to reduce negative symptoms of schizophrenia by change in Negative PANSS score and Motivation and Pleasure-Self Report (MAP-SR) score
 
Objective 3: To assess safety and tolerability of PEAR-004 by adverse event monitoring and InterSePT Scale for Suicidal Thinking-Plus (ISST-Plus) score
 
Objective 4: To evaluate the efficacy of PEAR-004 as an adjunct to existing clinician-directed pharmacotherapy to improve psychosocial functioning in patients with schizophrenia by change in World Health Organization Quality of Life (WHOQOL-BREF) scale
 
Objective 5: To evaluate the efficacy of PEAR-004 as an adjunct to existing clinician-directed pharmacotherapy to reduce depression symptoms in patients with schizophrenia by change in Beck Depression Inventory, Second Edition (BDI-II) score
 
Objective 6: To evaluate the magnitude of the effect of PEAR-004 as an adjunct to existing clinician-directed pharmacotherapy to reduce symptoms of schizophrenia by percentage improvement in PANSS score
 
Objective 7: To evaluate the response to treatment by the proportion of responders

	Objective 8: To evaluate patient adherence to antipsychotic medication by change in Brief Medication Questionnaire (BMQ)
Study design	This is a randomized, sham controlled, rater-blinded, parallel group trial. Patients will be randomized 1:1 to receive PEAR-004 or a sham control. The study includes an up to 4-week screening period, a 12-week treatment period, and a 4-week follow-up period.
Population	The study will enroll approximately 102 male and female adults (18-65 years of age, inclusive) with a diagnosis of schizophrenia

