
 • To evaluate the efficacy of PEAR-004 as an adjunct to existing clinician-directed pharmacotherapy to improve psychosocial functioning in patients with schizophrenia 	
 • Change on the World Health Organization Quality of Life (WHOQOL-BREF) scale from baseline to day 29, day 57, and day 85 or last visit

 • To evaluate the efficacy of PEAR-004 as an adjunct to existing clinician-directed pharmacotherapy to reduce depression symptoms in patients with schizophrenia 	
 • Change in the Beck Depression Inventory, Second Edition (BDI-II) total score from baseline to day 29, day 57, and day 85 or last visit

 • To evaluate the magnitude of the effect of PEAR-004 as an adjunct to existing clinician-directed pharmacotherapy to reduce symptoms of schizophrenia 	
 • Percentage change in PANSS score (within assigned group) from baseline to day 29, day 57, and day 85 or last visit

 • To evaluate the response to treatment 	
 • Proportion of responders, defined as a reduction of at least 20% at day 85 or last visit in total PANSS score relative to baseline

 • To evaluate patient adherence to antipsychotic medication 	
 • Change in antipsychotic pharmacotherapy use as measured by the Brief Medication Questionnaire (BMQ) at day 29, day 57, and day 85 or last visit

Exploratory Objectives

Corporate Confidential Information

Corporate Confidential Information

3 Study design

This is a randomized, sham controlled, rater-blinded, parallel group trial. Approximately 102 subjects will be randomized 1:1 in to the following groups:

- Group A: Clinician-directed pharmacotherapy + PEAR-004
- Group B: Clinician-directed pharmacotherapy + Sham application

An up to 28-day screening period will include standard screening assessments as defined in the assessment schedule. Eligible subjects will be randomized on day 1 into one of the treatment groups.

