Subjects in both groups will continue to receive their clinician-directed standard of care treatment for schizophrenia, including pharmacotherapy. Subjects in Group A will use PEAR-004 for a period of 12 weeks. Subjects in Group B will use a sham for a period of 12 weeks. Subjects will return to the clinic for outpatient visits at week 4 (day 29), week 8 (day 57), and week 12 (day 85). At each visit, standard assessments will be performed according to the assessment schedule, including PANSS, ISST-Plus, CGI, BMQ, MAP-SR, WHOQOL-BREF, BDI-II, ISI, and Adverse Events (AEs). A final follow-up visit will be performed at week 16 (day 115), including the assessments as detailed in the assessment schedule.

Figure 3-1 Study Design

4 Rationale

The overall rationale for the study is to assess the first PDT in schizophrenia using evidence-based coping skills to supplement standard of care with antipsychotic medications.

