9.1 Discontinuation

9.1.1 Discontinuation of study treatment

Discontinuation of study treatment for a subject occurs when study treatment is stopped earlier than the protocol planned duration, and can be initiated by either the subject or the investigator.

The investigator must discontinue study treatment for a given subject if, he/she believes that continuation would negatively impact the subject's well-being.

- Study treatment must be discontinued if the subject withdraws consent.

If discontinuation of study treatment occurs, the investigator should make a reasonable effort to understand the primary reason for the subject's premature discontinuation of study treatment and record this information.

Subjects who discontinue study treatment or who decide they do not wish to participate in the study further should NOT be considered withdrawn from the study UNLESS they withdraw their consent (see withdraw of informed consent section.). **Where possible, they should return for the assessments indicated** in the Assessment schedule (Table 8-1), especially the day 85 and EOS (day 115) visits. If they fail to return for these assessments for unknown reasons, every effort (e.g. telephone, e-mail, letter) should be made to contact the subject/pre-designated contact as specified in the lost to follow-up section. This contact should preferably be done according to the study visit schedule.

If the subject cannot or is unwilling to attend any visit(s), the site staff should maintain regular telephone contact with the subject, or with a person pre-designated by the subject. This telephone contact should preferably be done according to the study visit schedule.

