12.4 Analysis of the primary endpoint(s)

12.4.1 Definition of primary endpoint(s)

The primary efficacy endpoint in the study is change in total PANSS score from baseline to day 85 or last visit, analyzed using the FAS.

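### The three-month relocation exclusion names no start date and is shorter than study participation: it never reaches the day-115 visit and, counted from screening, can fall short of day 85

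*Protocol*

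**What the plan says.** Exclusion 2 in Protocol 5.2, repeated in the protocol summary, removes patients "Planning to move out of the geographic area within 3 months". No reference date is attached. Exclusion 1 in the same list, on antipsychotic changes, names both screening and randomization as reference points.

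On when eligibility is judged, Protocol section 5 states: "Subject selection is to be established by checking through all eligibility criteria at screening". Table 8-1 places the inclusion/exclusion check in the screening column only, with no repeat on day 1. Section 5 also tells sites: "No additional criteria should be applied by the investigator, in order that the study population will be representative of all eligible subjects".

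On the length of participation, the summary states: "The study includes an up to 4-week screening period, a 12-week treatment period, and a 4-week follow-up period". Section 3 fixes the last visit: "A final follow-up visit will be performed at week 16 (day 115), including the assessments as detailed in the assessment schedule". The primary PANSS endpoint is set at day 85 or last visit (12.4.1). Section 9.1.1 asks subjects who stop treatment to come back, "especially the day 85 and EOS (day 115) visits".

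**The concern.** A relocation exclusion is there to keep out patients who already know that they will not be available for the visits. This one uses a round number of months that is not tied to the visit schedule, and it does not say where the count begins.

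Three planned results depend on patients staying reachable:

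- **Day-85 total PANSS.** This is a clinician-administered interview, scheduled at clinic visits (sections 3 and 8.3.1).
- **Percent dropout.** This is listed beside PANSS as a primary endpoint, and the summary refers to it at the end of the study.
- **ISST-Plus at day 115.** This is listed as a secondary safety endpoint in Table 2-1.

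The sample size in 12.8.1 states no allowance for dropout: about 102 are randomized and Table 12-1 takes 102 as evaluable. Losses that an eligibility line could prevent are therefore worth preventing.

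**Working it through.** **Inputs.** Window: 3 calendar months, which is 89 to 92 days depending on the start date. Screening: s days before day 1, with s from 1 to 28 (Table 8-1, no day 0). Primary visit: day 85. Last visit: day 115.

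**Elapsed time.** From day 1, day 85 is 84 days away and day 115 is 114 days away. From screening, the distances are s + 84 and s + 114.

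**Counted from randomization**
- Day 85: 84 days against 89 to 92, so it is covered with 5 to 8 days to spare.
- Day 115: 114 − 92 = 22 and 114 − 89 = 25, so it is missed by 22 to 25 days.

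**Counted from screening**

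| Screening length s | Day 85 is at | Shortfall for day 85 | Day 115 is at | Shortfall for day 115 |
|---|---|---|---|---|
| 1 | 85 | none | 115 | 23 to 26 days |
| 5 | 89 | none | 119 | 27 to 30 days |
| 8 | 92 | 0 to 3 days | 122 | 30 to 33 days |
| 14 | 98 | 6 to 9 days | 128 | 36 to 39 days |
| 28 | 112 | 20 to 23 days | 142 | 50 to 53 days |

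Day 85 is always covered if s + 84 ≤ 89, that is s ≤ 5. It is never covered if s + 84 > 92, that is s ≥ 9. For s of 6 to 8 it depends on the calendar.

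**Where the window ends in the worst case.** With s = 28, it ends 89 − 28 = 61 to 92 − 28 = 64 days after day 1, which is study day 62 to 65. That is after the day-57 visit, so a patient who moves in the gap before day 85 has normally already given PANSS at days 29 and 57.

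**Effect on power.** First, the plan's own figure. With 51 per arm, difference 8, SD 16 and one-sided alpha 0.05, the normal approximation gives Φ(0.5·√(51/2) − 1.645) = Φ(0.880) = 81.1%. The noncentral t gives 80.6%. Section 12.8.1 says 80% and Table 12-1 says 81%, so the stated figure reproduces.

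The documents give no rate of planned moves. As an illustration only, suppose a share p of subjects lose day 85 but keep the earlier visits, and let ρ be the correlation of the day-57 and day-85 scores (assumed 0.5 to 0.8, not in the documents). The approximate effective size per arm is 51 / [ρ² + (1 − ρ²)/(1 − p)]. Example: p = 0.10 and ρ = 0.5 give 51 / (0.25 + 0.75/0.90) = 47.1.

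| Assumed share lost | Power, day 85 lost only (ρ = 0.5 to 0.8) | Power, no data at all from these subjects |
|---|---|---|
| 0% | 80.6% | 80.6% |
| 2% | 80.1 to 80.3% | 79.9% |
| 5% | 79.2 to 79.9% | 78.8% |
| 10% | 77.7 to 79.2% | 76.8% |

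All entries use the noncentral t. The last column is a worst case that the timeline does not support, because the earlier visits would have been collected.

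**The case against.** Four objections carry weight.

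1. **The start date is open.** If the three months run from randomization, day 85 is covered. This stands, so the day-85 gap is conditional. The day-115 gap is not. Screening is the more natural start because that is when the criteria are checked, but the criterion does not say so.

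2. **Exclusion 4 may already apply.** It removes patients unable to comply with study procedures for medical or other reasons, and section 9.2 requires each subject to complete the study. A site could use this for a known mover without adding a criterion. This stands in part. Relocation has its own criterion with its own limit, so a site could equally conclude that a move planned at three and a half months is allowed.

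3. **A move is not a dropout.** The app is on the subject's own phone, missed visits do not lead to automatic discontinuation (section 8), and subjects who stop treatment are asked back and otherwise followed by telephone (9.1.1). This stands. It is tempting to infer that known movers are plainly eligible and certain to be lost. The documents support only that they can be enrolled and may be lost.

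4. **Little harm to the primary analysis.** The SAP model (6.1.2) uses days 1, 29, 57 and 85, so the day-115 gap does not touch it. Moves planned before enrolment are expected equally in both arms and are compatible with the MAR assumption. This also stands. A reader might infer a loss of several points of power or a matching rise in dropout, but any such figure only restates an assumed rate that the documents do not give.

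**Conclusion.** The mismatch is real and minor. The three-month window does not reach day 115 on any count: it is short by 22 to 25 days from randomization and by up to 50 to 53 days from screening. It falls short of day 85 only if counted from screening and only when screening is long enough: always at 9 days or more, and by 20 to 23 days at most.

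The consequence is that some patients with a known move in the gap can enter and may miss the day-85 PANSS, add to the dropout endpoint, or miss the day-115 ISST-Plus. How many is unknown, and exclusion 4 may remove some of them. The likely loss of power is small and there is no evident bias. The stated sample size reproduces and is not in question. This is a cheap improvement to an eligibility line.

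**What to change.** In Protocol 5.2 and in the protocol summary, keep the opening of exclusion 2 and replace the three-month limit by 'before the day 115 visit'. Tying the rule to a visit settles the missing start date and the short window together.

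Do not add a number of months counted from screening as a gloss. With a 5-day screening, day 115 is 119 days after screening, while five calendar months are 150 to 153 days. A five-month limit would exclude patients who could complete every visit and would create a second, conflicting rule.

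The cost is one line in two places and slightly fewer eligible patients. The sample size and the analysis do not change.

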6.1 Study treatment

Details on the requirements for management of study treatment, and instructions to be followed for subject numbering, providing and utilizing study treatment are outlined in the SOM.

PEAR-004 is an investigational digital therapeutic, currently available on a mobile device (iOS and Android based). It is designed to serve as an illness self-management tool. Subjects can

access PEAR-004 as needed to receive suggestions about coping strategies to overcome difficulties in daily life.

A control sham will be available to the control group. The sham will be downloaded to the subject's phone, but will not deliver the active therapeutic content of PEAR-004. It will deliver notifications prompting the subject to open the sham app, and will then display a prescription timer for the remaining duration of app availability.

Eligible subjects will gain access to either PEAR-004 or sham according to their randomization assignment via a digital prescription access code provided to the site. Study site staff will receive training on how to download PEAR-004 or sham to the assigned subject's phone as part of site initiation activities.

6.1.1 Treatment arms/group

Subjects will be assigned on Day 1 to one of the following two treatment arms/groups in a ratio of 1:1

- PEAR-004
- Sham

6.2 Other treatment(s)

6.2.1 Concomitant therapy

Subjects are expected to maintain their physician prescribed pharmacotherapy during the study, as specified in the exclusion criteria.

All medications, procedures and significant non-drug therapies (including physical therapy and blood transfusions) administered after the subject is enrolled into the study must be recorded on the appropriate Case Report Forms.

6.3 Subject numbering, treatment assignment, randomization

6.3.1 Subject numbering

The subject number assigned to a subject at screening remains the unique identifier for the subject throughout the study. For information on subject numbering, please see 'Subject numbering' section in the Site Operations Manual.

6.3.2 Treatment assignment, randomization

The randomization numbers will be generated using the following procedure to ensure that treatment assignment is unbiased and concealed from raters at the site. A subject randomization list will be produced by the IRT provider, or by a delegate under Novartis supervision, using a validated system that automates the random assignment of subject numbers to randomization numbers. These randomization numbers are linked to the different treatment arms, which in turn are linked to treatment numbers. A separate treatment list will be produced using a validated system that automates the random assignment of treatment numbers.

The randomization scheme for subjects will be reviewed and approved by a member of the Randomization Office.

Follow the details outlined in the Site Operations Manual regarding the process and timing of treatment assignment and randomization of subjects.

6.4 Treatment blinding

This is a rater-blinded study. Raters will remain blinded to study treatment throughout the study.

The identity of the treatments will be concealed by limiting rater access to the randomization list, subject-specific phone, and web portal. Raters will be independent of other aspects of study conduct, and subjects will be instructed not to provide specific details about the content they are viewing on their phone to the rater.

All unblinded personnel will otherwise keep randomization lists and data or information that could unblind the rater confidential and secure until clinical database lock.

Following final database lock all roles may be considered unblinded. See the blinding/unblinding table for an overview of the blinding/unblinding plan.

Table 6-1 Blinding and unblinding plan

Role	Time or Event			
	Randomization list generated	Treatment allocation	Safety event (single subject unblinded)	Interim Analysis
Subjects	UI	UI	UI	UI
Site staff	UI	UI	UI	UI
Raters (independent of other aspects of study conduct)	B	B	B	B
Randomization Office	UI	UI	UI	UI
Unblinded sponsor staff	UI	UI	UI	UI
Unblinded Pharmacovigilance sponsor staff	NA	NA	NA	NA
Statistician/statistical programmer/ data analysts (e.g. biomarker)	UI	UI	UI	UI
Independent committees used for assessing interim results, if required (e.g. DMC)	NA	NA	NA	NA
All other sponsor staff not identified above (trial team, project team, management & decision boards, support functions)	UI	UI	UI	UI

UI: Allowed to be unblinded on individual subject level

B: Remains blinded

NA: Not applicable to this study

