8.3 Efficacy

8.3.1 Positive and Negative Syndrome Scale (PANSS)

The PANSS is a 30-item clinician-administered semi-structured interview of schizophrenia symptoms. The PANSS total score can be further broken down to subscales for positive, negative, and general symptoms.

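### The instruction on what subjects may tell the blinded rater covers app content only, so a subject can name the arm in the PANSS interview without breaking it

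*Protocol*

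**What the plan says.** Protocol section 6.4 sets the level of masking: "This is a rater-blinded study. Raters will remain blinded to study treatment throughout the study". In Table 6-1 raters are the only role marked B. Subjects are marked UI at every listed time or event, and the key defines the code as "UI: Allowed to be unblinded on individual subject level".

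Section 6.4 protects the raters in four ways:

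- Treatment identity is "concealed by limiting rater access to the randomization list, subject-specific phone, and web portal".
- On the rater's role, it says: "Raters will be independent of other aspects of study conduct".
- For speech between subject and rater, "subjects will be instructed not to provide specific details about the content they are viewing on their phone to the rater".
- A confidentiality duty is placed on those who know the assignment: "All unblinded personnel will otherwise keep randomization lists and data or information that could unblind the rater confidential and secure until clinical database lock".

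The primary efficacy endpoint is the change in total PANSS (Protocol 12.4.1, SAP 6.1). Protocol 8.3.1 describes the instrument: "The PANSS is a 30-item clinician-administered semi-structured interview of schizophrenia symptoms". Table 8-1 schedules it after baseline at days 29, 57 and 85, and again at day 115.

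The two apps differ plainly to the user. Protocol 1.1 describes PEAR-004 as offering skills in several symptom areas, among them voices, thoughts, mood and sleep. For the sham, Protocol 4.3 says that "when the app is opened it will display a prescription timer for the remaining duration of app availability".

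**The concern.** The instruction restricts one kind of remark, namely detail about what is on the screen. It does not ask subjects to withhold which app they were given, which one they believe they have, whether they use it, or whether it helps. The PANSS interview asks about symptoms that the active app addresses, so the app can come up without anyone intending to unblind the rater.

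If raters learn the arm for some subjects and score differently as a result, the difference enters the primary contrast directly. The mixed model cannot remove it. The two sensitivity analyses in Protocol 12.4.4.1 and SAP 6.1.2.1 are described as addressing missing data, not rating bias. Nor does the visible text plan any record of such disclosures, so a positive result would invite a question about the raters that the visible data could not answer.

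**Working it through.** **Step 1. Does any safeguard cover what a subject says?**

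| Safeguard (Protocol 6.4) | What it controls | Stops a subject naming the arm? |
|---|---|---|
| Limited access to list, phone and portal | What the rater can look up | No |
| Rater independence | The rater's other duties | No |
| Confidentiality duty | What unblinded personnel disclose; subjects are not named | Not clearly |
| Instruction to subjects | Specific details of app content | Only if the remark describes content |

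Protocol 6.3.2 also conceals assignment from raters, but through the randomization process, not through the subject.

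**Step 2. Which remarks get through?**

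- Stating that one has the sham, or the real app: names the arm, gives no content, not barred.
- Saying that the app only shows a timer: identifies the arm, but can be read as a content detail and so may already be barred.
- Saying that the app helped with voices: touches a content area, so arguably barred.
- Saying that the app does nothing, or how often it is used: not barred, but not decisive about the arm either.

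The gap is therefore narrow but real: naming the arm, or implying it strongly in general terms.

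**Step 3. Reproduce the design.** Inputs from Protocol 12.8.1: 102 subjects at 1:1 (51 per arm), SD 16, difference 8, one-sided alpha 0.05.

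- SE of the difference = 16 × √(2/51) = 3.168 points.
- Noncentrality = 8 / 3.168 = 2.525.
- Power = 80.6% from the noncentral t with 100 df, or 81.1% from the normal approximation.

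The text states 80% and Table 12-1 states 81%, so the design reproduces.

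**Step 4. Illustrate the effect of a rating shift.** The documents give no frequency of disclosure and no size of rating bias, so both are assumed. Let the arm be revealed in a fraction f of subjects in each arm, and let the scored between-arm difference move by m points among them in favor of PEAR-004. Then the mean shift is b = f × m. With a true difference of zero, the chance of a significant result is the upper tail of a noncentral t with 100 df and noncentrality b / 3.168, beyond the one-sided 5% critical value.

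| f | m (points) | b = f × m | b / 3.168 | One-sided type I error |
|---|---|---|---|---|
| 0 | – | 0 | 0 | 5.0% |
| 5% | 4 | 0.2 | 0.063 | 5.7% |
| 10% | 4 | 0.4 | 0.126 | 6.4% |
| 20% | 4 | 0.8 | 0.252 | 8.2% |
| 20% | 8 | 1.6 | 0.505 | 12.6% |
| 30% | 8 | 2.4 | 0.757 | 18.6% |

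The last two rows use m = 8, a rating shift as large as the whole treatment effect assumed in Protocol 12.8.1, and should be read as an upper illustration. The first rows are close to nominal. The table uses a two-sample comparison with all 102 subjects evaluable, not the mixed model.

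**The case against.** The strongest reply is that the blind has several layers. A reader might infer that it depends wholly on subjects' discretion. Section 6.4 does not support that, since access limits, rater independence and the confidentiality duty all stand. What remains is that none of them governs what the subject says.

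A reader might also infer that subjects are told their arm. Table 6-1 says only that they are allowed to be unblinded, so naming the arm requires either being told or a correct guess. With a sham that shows only a timer, a correct guess is plausible, but the documents do not establish how often it would happen.

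It is tempting to say that any general remark gives the arm away, or that a notification during the interview does. Neither holds. A dissatisfied PEAR-004 user could also say that the app does nothing, and Protocol 1.1 and 4.3 give both apps three notifications a day.

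Fuller instructions may exist. The protocol sends operational detail to a Site Operations Manual that is not among the documents, and parts of Table 8-1 and section 8.5 are redacted. This limits any claim that a script or disclosure record is absent. It does not change the rule printed in section 6.4, which does not refer to the manual for blinding and is too narrow as written.

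Finally, the size of the bias is assumed, and its direction need not be the same for every subject. That objection stands in full.

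**Conclusion.** The point holds as a gap in one safeguard: as worded, the instruction lets a subject name or strongly imply the arm to the only blinded role during the primary assessment. This follows from the text and needs no assumption about behavior.

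The consequence does need assumptions. Neither the frequency of disclosure nor the resulting rating shift can be derived from the documents. Over an assumed mean shift of 0.2 to 2.4 points, the one-sided type I error runs from about 5.7% to 18.6%; the low end is negligible and the high end is not. These figures take 51 per arm, SD 16, no true effect and a shift that consistently favors PEAR-004.

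A reader might go further and conclude that the blind will fail, or that the trial could not show that it held. The documents do not support the first, and the unseen manual and the redactions prevent the second from being stated as fact. The change is worth making because the rule is easily widened, not because bias has been shown.

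**What to change.** Replace the instruction in Protocol 6.4 with wording such as: *Before each rating, subjects will be told not to mention the study app to the rater at all, including which app they have, whether or how often they use it, and whether it helps. The rater will open each interview with a scripted reminder of this.*

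Add one CRF item, completed by the rater after each PANSS at days 29, 57 and 85, recording whether the arm was disclosed. Add a line to the SAP to tabulate it by arm and visit.

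A rater's guess of the arm is optional. It is confounded with efficacy, because a rater who sees improvement may guess PEAR-004, so it should be interpreted with caution and does not replace the disclosure item.

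The cost is one reworded sentence, a short script, one CRF item per rating and one table. The small downside is that subjects cannot mention the app when the interview turns to coping; feedback about the app goes to unblinded site staff instead. Sample size, visits and the primary model are unchanged.
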